6.2. Treatment Period

After signed the ICF within 28 days, the eligible subjects must start treatment as soon as possible. For all subsequent visits, an administrative window of \pm 3 days is permitted, otherwise specified.

Subjects will receive a single dose of ATG-008 on Day -1, followed by a 48-hour observation for PK sample collection.

- Oral daily dosing of 15 mg or 30 mg begin on Day 1 and will continue in 28-day cycles
- It is planned that approximately 20 subjects will receive oral ATG-008 at an initial dose of 45 mg/QD and another 20 subjects will receive oral ATG-008 at an initial dose of 20 mg/BID. The 28 continuous days are regarded as one treatment cycle. The pharmacokinetic (PK) samples will be collected from 10 subjects each in the two dose groups.

The subjects will continue to use ATG-008 until radiologic disease progression, intolerable toxicities, or withdrawal of consent for further dosing (in which case subjects will continue to be followed for further anticancer treatment and survival status unless consent for this has been explicitly withdrawn). Subjects will fast ≥ 6 hours before those clinical visits which require evaluation of PK and fasting chemistry examination. PK, safety and tolerability for the 30-mg dose level will follow the assessment of the 15-mg dose level if DLTs occur in less than 2 of 6 subjects at the 15-mg dose level who complete Cycle 1.

The following evaluations will be performed at the frequency specified in the Table of Events, [Table 3](#). The evaluations should be performed prior to dosing on the visit day, unless otherwise specified.

- Adverse event evaluation (continuously)
- Concomitant medications evaluation (including medications for best supportive care)
- Concomitant procedures evaluation
- ECOG performance status
- Vital signs, weight
- Hematology laboratory
- Coagulation panel
- Fasting chemistry laboratory
- Special chemistry laboratory
- HbA1c
- Urine routine
- AFP
- HBV viral load (in subjects with positive HBsAg, HBeAg HBcAb or positive viral load at screening).
- Urine β -hCG (females of childbearing potential (FCBP) only)
- Radiologic response assessment/tumor evaluation and assessment of disease progression (see Section 6.4)

- PK sampling (see Section 6.5)

Detailed evaluations are listed in [Table 3](#).

6.2.1 End of Treatment

An end of treatment (EOT) evaluation should be performed for subjects who are withdrawn from treatment for any reason as soon as possible after the decision to permanently discontinue treatment has been made.

The following evaluations will be performed as specified in the Table of Events:

- Adverse event evaluation
- Concomitant medications evaluation
- Concomitant procedures evaluation
- Vital signs and weight.
- Hematology laboratory
- Fasting chemistry laboratory
- AFP
- 12-lead ECG, single local assessment
- Urine β -hCG (FCBP only)

For subjects who discontinue study drug for reasons other than radiologic progression (or withdrawal of consent for additional follow-up procedures), tumor evaluations will be continued at the schedule defined in the Table of Events [Table 3](#), and do not need to be performed specifically for the EOT visit.

6.3. Follow-up Period

6.3.1 28-day Follow-up

All subjects will be monitored for reporting of new or follow-up of existing AEs for 28 days after the last dose of study drug. Any clinically relevant assessments or laboratory parameters should have unscheduled assessments conducted until resolution, at the discretion of the Investigator.

6.3.2 Efficacy Follow-up

All subjects who discontinue treatment for reasons other than disease progression, death or withdrawal of consent for post-treatment follow-up procedures will continue to undergo response assessments and collection of new anticancer therapies as specified in Section [6.4](#).

6.3.3 Survival Follow-up

After the last dose of study drug, all subjects will be followed every 8 weeks (\pm 1 week) for survival until death or lost to follow-up. Even when subjects withdraw consent for further treatment, every effort should be made to obtain post-treatment follow-up information which includes new anticancer therapies and survival status.

Survival follow-up may be conducted by record review and/or telephone contact with the subject, family or the subject's treating physician.

6.4. Response Assessments

Tumor response assessments should be performed in Screening (up to 28 days before the start of study drug) and every 8 weeks (\pm 5 days) from the first dose date until disease progression, death or withdrawal of consent from additional follow-up procedures. Tumor

assessments includes imaging (CT or MRI) of the chest, abdomen and pelvis at baseline. Subjects with brain lesions will have brain scans at screening and at each tumor assessment. After Screening, tumor assessments will be performed on completion of C2, C4 and C6 (i.e., C3, 5 and 7/Day1±7 days) using the same scanning modalities used at baseline. Corticosteroids (if used) dosage must be stable \geq 5 days prior to all scans. EOT scan need not be repeated if prior scan was $<$ 28 days.

If a subject discontinues study drug due to toxicity, subject or physician decision, the collection of response assessments should continue at the same schedule. Additionally, if a subject continues treatment beyond radiologic disease progression until symptomatic deterioration (see Appendix A, Section 19.1.2.4), tumor evaluations should continue until study drug is stopped. Evaluation of response should be performed using RECIST 1.1 guidelines.

New anticancer therapy includes any systemic medication, locoregional therapy, surgery, radiation or any other therapy intended to treat the subject's cancer.

6.4.1 Assessment of Radiologic Response According to RECIST 1.1

Response will be assessed using RECIST 1.1 Appendix. Response assessments (tumor evaluations) include computed tomography (CT) scan or magnetic resonance imaging (MRI). The regions to be imaged are the chest, abdomen and pelvis, as well as any other region clinically indicated for tumor imaging. Subjects with brain metastases will have brain scans at Screening and at each tumor reassessment. The same mode of imaging for lesion evaluation at screening must be consistently used throughout the study.

The CT imaging should include contrast unless medically contraindicated. Conventional CT should be performed with contiguous cuts of 5 mm or less in slice thickness. Spiral CT should be performed by use of a 5 mm contiguous reconstruction algorithm.

All subjects with evidence of radiologic tumor response (CR or PR) should have the response confirmed with repeat assessments at the next scheduled scan, but after no less than 28 days. Response assessments must have occurred \geq 5 weeks from the first dose date to be considered as SD for a best response.

The Investigators will evaluate RECIST 1.1 response after each restaging and overall assessment. All related scans will be collected and saved for future independent central review.

If ORR of tumor is greater than 15% in the study dose group (45 mg/QD or 20 mg/BID), then this study will be expanded to enroll additional approximately 110 subjects using ORR as the primary study endpoint, to further evaluate the efficacy and safety of ATG-008.

All scans will be collected and then be reviewed centrally for independent analysis of ORR and other objective tumor response outcomes. mRECIST will then also be applied in tumor assessment, if necessary.

Additional details and definitions of response according to RECIST 1.1 are found in Appendix A in Section 19.1.

6.5. Pharmacokinetics

PK blood samples (2 mL/sample) will be collected from each subject as described in Table 3.

For all PK draws, the following information will be documented: The dose of study drug administered, the actual time of study drug dosing, the actual time of each PK sample collection, and the nominal or scheduled time for PK sample collection. The laboratory manual includes procedures for collecting, processing, storing, and shipping PK samples.

6.5.1 Intense Blood Sampling

A total of 30 subjects will undergo intense PK sampling; 6 subjects at the 15-mg dose and 24 subjects at the 30-mg dose level.

As for the 2 dose groups 45 mg/QD and 20 mg/BID, PK samples of 10 subjects each should be collected.

Blood (2 mL/sample) will be drawn at the following times in Cycle 1.

Sampling time points for subjects received ATG-008 at the initial doses of 15 mg, 30 mg and 45 mg/QD:

On Day -1: 0hr (< 15min prior to dosing), 0.5hr ± 5 mins, 1hr ± 10mins, 1.5hr ± 10mins, 3hr ± 10mins, 5hr ± 15mins, 8hr ± 30mins, 24hr ± 60mins and 48hr ± 60mins after the first dose of ATG-008

On Day 15: 0hr (< 15min prior to dosing), 0.5hr ± 5mins, 1hr ± 10mins, 1.5hr ± 10mins, 3hr ± 10mins, 5hr ± 15mins, 8hr ± 30mins and 24hr ± 60mins after the Day 15 dose.

Sampling time points for subjects received ATG-008 at the initial dose of 20 mg/BID:

At Day -1: 0hr (15 minutes before dosing); the first dose of 20 mg: 0.5hr ± 5min, 1hr ± 10min, 1.5hr ± 10min, 3hr ± 10min, 5hr ± 15min, 8hr ± 30min and 12hr ± 30min; second dosing of 20 mg: 12hr ± 30min after dose of ATG-008;

At Day 15: 0hr (15 minutes before dosing); the first dose of 20 mg: 0.5hr ± 5min, 1hr ± 10min, 1.5hr ± 10min, 3hr ± 10min, 5hr ± 15min, 8hr ± 30min and 12hr ± 30min after dose of ATG-008;

When study drug dosing has been interrupted before the Day 15 assessments, PK sampling should be delayed until ATG-008 has been administered continuously for at least 7 days in order to more accurately determine steady state kinetics.

After Day 15, if the dose of ATG-008 is reduced and (optional) subject consent is obtained, approximately 10 days later blood will be withdrawn for additional PK assessments at the following times in order to conduct intrasubject assessment of PK at lower dose levels: Predose (< 15mins prior to dosing), 1hr ± 10mins, 1.5hr ± 10mins, 3hr ± 10mins, and 5hr ± 15mins.

6.5.2 PK urine collection

Urine sampling time points for subjects received ATG-008 at the initial doses of 15 mg, 30 mg and 45 mg/QD:

Total urine collections for PK analysis on Day -1 through Day 0 will be taken over the following times: Predose (<30 minutes prior to dosing, to completely empty the bladder), 0-4 hr and 4-8 hr and 8-24 hr.

Urine sampling time points for subjects received ATG-008 at the initial dose of 20 mg/BID:

At Day -1: 0hr (30 minutes prior to dosing), 0-4 hr, 4-8 hr and 8-12 hr after the first dose of ATG-008;

7. STUDY POPULATION

7.1 Number of Subjects

The 35 HBV+, unresectable HCC subjects who have received at least one prior line of systemic therapy have been enrolled in this study.

According to the previous study results, the sponsor plans to continue to enroll approximately 40 subjects to receive ATG-008 at an initial dose of 45mg/QD or 20 mg/BID.

If ORR of tumor is greater than 15% in the study dose group (45 mg/QD or 20 mg/BID), this study will be expanded to enroll additional approximately 110 subjects using ORR as the primary study endpoint, to further evaluate the efficacy and safety of ATG-008.

7.2 Inclusion Criteria

Subjects must meet all the following criteria to be enrolled in the study:

1. Male or female aged from 18 to 70 years (inclusive) at the time when the ICF is signed.
2. Confirmed pathologic or radiologic diagnosis of HCC according to the American Association for the Study of Liver Disease (AASLD) guidelines.
3. Unresectable stage B (intermediate) or C (advanced) HCC according to the Barcelona Clinic Liver Cancer (BCLC) staging. If stage B, the subject must have progressed after, or not be eligible for, surgical or locoregional therapy.
4. There is at least one measurable lesion according to RECIST 1.1 criteria.
5. HBV+ is defined as chronic HBV infection or a history of HBV infection, based on any of the following serologic results: HBcAb+, HBsAg+, HBV-DNA+.
6. Received at least one prior line of systemic therapy (with radiologic disease progression during or following sorafenib and/or chemotherapy). Subjects with alternative treatments such as regorafenib and/or anti PD-1 antibodies etc. approved by local health authorities are allowed to enter study if they meet all other inclusion/exclusion criteria.
 - a. Chemotherapy is defined FOLFOX (fluorouracil, leucovorin and oxaliplatin), or any other platinum-containing regimen.
 - b. Chemotherapy \geq two cycles
7. ECOG performance status score of 0 or 1.
8. Serum chemistry results, evidenced by the following:
 - a. AST (SGOT) and ALT (SGPT) \leq 5x upper limit of normal range (ULN).
 - b. Total bilirubin \leq 2 x ULN.
 - c. Creatinine \leq 1.5 x ULN or 24-hour clearance \geq 50 mL/min.
 - d. Lipase and amylase \leq 2 x ULN;
9. Adequate bone marrow function, evidenced by the following:
 - a. Absolute neutrophil count (ANC) \geq 1.5 \times 10⁹ cells/L.
 - b. Platelets \geq 75 \times 10⁹ cells/L.

- c. Hemoglobin ≥ 9 g/dL.
- 10. Coagulation function: international normalized ratio (INR) ≤ 2.0 , prothrombin time (PT) $\leq 1.5 \times$ ULN;
- 11. Child-Pugh A and B7 and hepatic encephalopathy scored as 1 point;
- 12. Except hearing loss and alopecia, all toxicities caused by previous anti-tumor therapies must recover to \leq Grade 1 (based on NCI-CTCAE Version 4.03);
- 13. Male subjects (including those who have had a vasectomy) must agree to use a condom during sexual intercourse with females of child-bearing potential, and shall not conceive a child starting from the time of ICF signature, while on study medication, and for 3 months after the last dose of study drug.
- 14. Female subjects of child-bearing potential must have both of the following:
 - a. Agree to the use of two study physician-approved contraceptive methods simultaneously or practice complete abstinence starting at the time of ICF signature, while on study medication, and for 28 days following the last dose of study drug.
 - i. True abstinence: When this is in line with the preferred and usual lifestyle of the subject. Periodic abstinence (e.g., calendar, ovulation, symptothermal, post-ovulation methods) and withdrawal are not acceptable methods of contraception.
 - ii. Acceptable contraceptive methods include: Oral, injectable, or implantable hormonal contraceptive; intra-uterine device; barrier contraceptive with spermicide; or vasectomized partner, together with at least one barrier method.
 - b. Have negative serum pregnancy test result at Screening confirmed by negative urine pregnancy test within 72 hours prior to first dose of study drug (if serum test occurred > 72 hours from first dose); pregnancy test must have a sensitivity of at least 25 mIU/mL.

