- Prior and concomitant medication evaluation (includes those taken ≤ 28 days before the screening visit, except those taken for cancer which are recorded as part of prior cancer therapy).
- Prior and concomitant procedures (includes all procedures occurring ≤ 28 days before the screening visit).
- Adverse event evaluation (begins when the subject signs the informed consent form [ICF]).
- Vital signs (including blood pressure, temperature and pulse).
- Hematology: Complete blood count (CBC) with differential, including red blood cell (RBC) count, hemoglobin, hematocrit, white blood cell (WBC) count with absolute differentials (neutrophils, lymphocytes, monocytes, eosinophils and

basophils), and platelet count; within 7 days of the first dose of study drug.

- Coagulation panel: Prothrombin time (PT), international normalized ratio (INR), partial thromboplastin time (PTT); within 7 days of the first dose of study drug.
- Fasting chemistry laboratory: Includes sodium, potassium, chloride, calcium, magnesium, phosphorus, glucose, blood urea nitrogen (BUN), creatinine, albumin, total protein, alkaline phosphatase, bilirubin (total and direct), aspartate amino transferase (AST/SGOT), alanine amino transferase (ALT/SGPT), lactate dehydrogenase (LDH), uric acid, cholesterol and triglycerides; within 7 days of the first dose of study drug.
- Special chemistry laboratory: Amylase, lipase, thyroid stimulating hormone (TSH), free T4 (fT4); within 7 days of the first dose of study drug.
- Hemoglobin A1c (HbA1c) within 7 days of the first dose of study drug.
- AFP.
- Hepatitis B virus (HBV) and hepatitis C virus (HCV) serologies (hepatitis B surface antigen [HBsAg], hepatitis B e antigen [HBeAg], hepatitis B surface antibody [HBsAb], hepatitis B e antibody [HBeAb], hepatitis B core antibody [HBcAb], hepatitis C virus antibody [HCVAb]).
- HBV viral load.
- Urine routine within 7 days of the first dose of study drug.
- 12-lead electrocardiogram (ECG), single local assessment; when an ECG time-point coincides with any other assessment, the ECG should always be collected first.
- Pregnancy test (β -hCG) is required for all female subjects of child-bearing potential. Serum β -hCG pregnancy test will be performed at screening. A urine (or local serum) pregnancy test will be performed to assess subject eligibility within 72 hours prior to the first administration of study drug.

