19.4.2 Child-Pugh Classification of Liver Failure

Subjects with Child-Pugh A and B7 and hepatic encephalopathy scored as 1 point meet this individual inclusion criterion for the study.

Table 7: Child-Pugh Classification

	1 point	2 points	3 points
Bilirubin (mg/dL)	< 2	2-3	> 3
Albumin (g/L)	> 3.5	2.8-3.5	< 2.8
Prothrombin time prolonged in seconds (INR)	1-4 (< 1.7)	4-6 (1.7-2.3)	> 6 (> 2.3)
Ascites	None	Slight	Moderate
Hepatic encephalopathy	None	Grade 1-2	Grade 3-4
Child A: 5-6 points; Child B: 7-9 points; Child C: ≥ 10 points			

Source: [Pugh, 1973](#)

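### Table 7 labels albumin in g/L beside cut-offs of 3.5 and 2.8, so a site applying it literally to g/L results could pass some Child-Pugh B8 or B9 subjects under inclusion 11

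*Combined protocol and SAP*

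**What the plan says.** Inclusion 11, in the synopsis and in Section 7.2, admits "Child-Pugh A and B7 and hepatic encephalopathy scored as 1 point". It does not cite a scoring table. Section 19.4.2 supplies the link: it repeats the rule, states that such subjects "meet this individual inclusion criterion for the study", and then prints Table 7 with its published source.

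In Table 7 the bilirubin row is in mg/dL. The albumin row is in g/L, with 1 point above 3.5, 2 points from 2.8 to 3.5, and 3 points below 2.8. The classes are "Child A: 5-6 points; Child B: 7-9 points", with C from 10 points.

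Albumin is measured at screening as part of the fasting chemistry (Section 6.1: "creatinine, albumin, total protein, alkaline phosphatase"), with no unit given. Laboratory work is done at site unless otherwise specified. Inclusion 8 limits transaminases, bilirubin, creatinine, lipase and amylase, but not albumin. No other section gives an albumin limit, a conversion or a second Child-Pugh table.

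**The concern.** In g/L, the 2-point and 3-point albumin bands begin at 3.5 and lie about a tenth of the way up the scale on which albumin is actually found. Applied literally to g/L results, the row gives everyone 1 point, and one of the five components of the score stops discriminating. Child-Pugh is the only route by which albumin bears on entry, so nothing else would catch the error.

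Two things are at stake. The first is the intended ceiling on hepatic impairment, in a trial of a drug metabolised mainly by CYP3A4/5 (Section 9.3). The second is the per-protocol set, which requires that all eligibility criteria were met (Section 10.2.2): a score that is too low would pass that check unnoticed. Section 10.6.3 also lists albumin among the baseline prognostic variables.

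**Working it through.** The plan states no figure of its own to reproduce here. The check compares Table 7 as printed with the same cut-off figures read per decilitre.

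**Step 1: albumin points.** The documents give no physiological range; 15 to 50 g/L is assumed.

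| Albumin (g/L) | Points as printed | Points with cut-offs read per decilitre |
|---|---|---|
| 36 to 50 | 1 | 1 |
| 28 to 35 | 1 | 2 |
| 15 to 27 | 1 | 3 |

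The middle column is the same for any albumin above 3.5 g/L, so it does not depend on the assumed range.

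**Step 2: effect on the total.** Printed total = per-decilitre total − (albumin points − 1). Entry requires a total of 7 or less.

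- B8 with 2 albumin points: 8 − 1 = 7, eligible.
- B8 with 3 albumin points: 8 − 2 = 6, eligible as A.
- B9 with 3 albumin points: 9 − 2 = 7, eligible.
- B9 with 2 albumin points: 9 − 1 = 8, still ineligible.
- B8 or B9 with 1 albumin point: unchanged, ineligible.
- C10 with 3 albumin points: 10 − 2 = 8, still ineligible.

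**Step 3: what the other criteria leave open.**

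- Encephalopathy: 1 point (inclusion 11; exclusion 2).
- Bilirubin: at most 2 × ULN (inclusion 8b). The ULN is not given. At an assumed 1.2 mg/dL the limit is 2.4 mg/dL, so 1 or 2 points. At 1.0 mg/dL it is 2.0 mg/dL, so 2 points arise only at exactly 2.0.
- Coagulation: INR up to 2.0 reaches the 2-point band (1.7 to 2.3), but inclusion 10 also caps PT at 1.5 × ULN. The PT ULN is not given; this cap may hold the component to 1 point.
- Ascites: a small amount seen only on imaging is allowed (exclusion 14), taken as 1 or 2 points.
- Albumin: 1, 2 or 3 points.

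**Step 4: enumeration, widest case.** Bilirubin, coagulation and ascites at 1 or 2 each, albumin at 1 to 3: 2 × 2 × 2 × 3 = 24 patterns. Let S be the sum of the first three. S = 3, 4, 5, 6 occurs 1, 3, 3, 1 times.

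- As printed: total = S + 1 + 1, so S ≤ 5 is eligible. That is 7 × 3 = 21 patterns.
- Per decilitre: total = S + 1 + albumin points. Albumin 1 needs S ≤ 5 (7 patterns), albumin 2 needs S ≤ 4 (4), albumin 3 needs S = 3 (1). That is 12 patterns.
- Difference: 21 − 12 = 9, of which 6 are B8 and 3 are B9. The 24 patterns include 11 at B8 or B9 (7 and 4), so 2 of those 11 remain excluded.

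**Step 5: narrower cases.**

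| Assumption | Patterns | Eligible as printed | Eligible per decilitre | Extra |
|---|---|---|---|---|
| Bilirubin and coagulation 1 or 2 | 24 | 21 | 12 | 9 (6 B8, 3 B9) |
| Coagulation held to 1 | 12 | 12 | 8 | 4 (3 B8, 1 B9) |
| Coagulation and bilirubin held to 1 | 6 | 6 | 5 | 1 (1 B8) |

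All three rows count imaging-only ascites as slight (2 points). If a site scored it as none in the last case, the highest total would be 1 + 1 + 1 + 1 + 3 = 7 and no pattern would change status.

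**The case against.** The strongest reply is that the misprint is too visible to do harm. The cut-offs are impossible in g/L, inclusion 11 names a standard score without citing Table 7, and the table names its source. A site reporting in g/dL would compare 3.2 with 3.5 and score it as a per-decilitre table would. Eligibility questions go to the medical monitor (Section 6.1), and monitoring must verify adherence to the entry criteria (Section 16.1). All of this stands, and it makes the effect conditional: it needs g/L results and literal use of the table. It does not make the printed threshold correct, and the documents do not show how sites scored.

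Three stronger readings are tempting.

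- A reader might infer that B8 and B9 subjects in general get in. They do not: B8 or B9 with 1 albumin point, and B9 with 2, stay out.
- A reader might infer that ORR, PFS and OS are diluted. The documents give no albumin distribution and no outcome by Child-Pugh score. The bilirubin, INR and PT caps, the ascites and encephalopathy exclusions, ECOG 0 or 1 and the life-expectancy exclusion also limit how much hepatic impairment could enter, although none of them replaces albumin.
- A reader might infer that the 35 subjects already treated include eligibility deviations. They were enrolled by 18 Jul 2019 (Section 4.2), before V2.0 of 30 Aug 2019. The V1.0 criterion and table are not available to check, and these subjects are outside the 130 (20 + 110) in the ORR test of Section 10.3.

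**Conclusion.** The point holds as an error in the only table that supports an entry criterion, with a conditional consequence. As printed, the albumin row cannot discriminate for results in g/L. A site applying it literally would admit some B8 subjects (2 or 3 albumin points) and some B9 subjects (3 albumin points) as A or B7.

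The size is 1 of 6 to 9 of 24 score patterns. The range rests on an assumed bilirubin ULN of 1.0 to 1.2 mg/dL, on whether the PT limit holds coagulation to 1 point, and on scoring imaging-only ascites as slight. How many subjects are affected depends on how many have albumin of 35 g/L or less, which the documents do not give.

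The sample size is untouched. The primary ORR analysis uses all treated subjects whatever their eligibility, so its analysis set does not change; only the supportive per-protocol set could. A correction is worth making because about 40 more subjects are planned, with about 110 further if the study expands.

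**What to change.** Reconcile the albumin unit and cut-offs in Table 7 with the classification it cites, before further enrolment, and have inclusion 11 refer to the table explicitly.

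For subjects enrolled under V2.0, check the screening Child-Pugh score against the reconciled table using albumin, bilirubin, INR/PT and ascites status, all already on file. Ascites must be included because it is a scored component. Apply the result when forming the per-protocol set. For the 35 earlier subjects, check against the protocol version in force when each enrolled, and do not label them deviations under V2.0.

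The cost is a one-line protocol correction and a check of existing data. The small downside is that a few subjects may leave the per-protocol set.
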